## A Introduction

#### A1 Study Abstract

Oral naltrexone was initially FDA approved to treat opioid use disorder and alcohol dependence at doses from 50-100mg/day. At lower doses of 1-5mg/day, naltrexone has been used off-label with success in treatment of several dermatologic conditions including the scarring alopecia (irreversible hair loss), lichen planopilaris. A recent case series of four patients with lichen planopilaris and a subtype, frontal fibrosing alopecia, treated with oral low-dose naltrexone at 3mg daily showed reduction of itch, clinical evidence of inflammation of the scalp, and of disease progression. There were no reported adverse events.

Based on the promising evidence, we propose using low-dose naltrexone at a daily dose of 3mg to treat lichen planopilaris and frontal fibrosing alopecia. The patients would be continued on their other medications for these conditions. The study would be openlabel, so all participants would receive the low-dose naltrexone. Patients would be seen at monthly intervals over a period of six months to monitor their progress.

### A2 Primary Hypothesis

Does daily oral low-dose naltrexone (3mg per day) reduce symptoms and disease progression in patients with lichen planopilaris and frontal fibrosing alopecia?

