#### B2 Rationale for this Study

While initial studies using LDN for dermatologic conditions is promising, the level of evidence is low, generally limited to case reports and series. Based on case reports, we expect the participant to benefit though decrease in their symptoms (burning, itching) as well as decreased redness and scale and possibly slowing or halting disease progression.

This increased data would benefit society by providing further evidence for the use of low-dose naltrexone in lichen planopilaris and frontal fibrosing alopecia.

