## E Study Design

#### E1 Overview or Design Summary

Uncontrolled open-label prospective study

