#### E2 Subject Selection and Withdrawal

#### 2.a Inclusion Criteria

Adults age 18 or greater with clinically or histologically confirmed diagnosis of lichen planopilaris or frontal fibrosing alopecia are eligible.

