#### 2.c Subject Recruitment Plans and Consent Process

Patients will be recruited from the pool of patients seen at Washington University/BJH dermatology clinics with existing and new diagnoses of lichen planopilaris and frontal fibrosing alopecia. Recruitment will be by word of mouth. Participants will be adequately informed about the study and have an opportunity to ask questions prior to enrollment. They will be seen during routine dermatology clinic visits and evaluated per protocol to determine eligibility for the study. Patients will have an opportunity to read and take home the consent form. Enrollment will be on a rolling basis between September 1st and October 31st, 2019. Patients who enroll in the study will be followed in [name] dermatology clinic at [name] (BJH West County). We will confirm with patients that they have decision-making capacity and the ability to understand the risks and benefits of the treatment.

Patients who do not respond to the invitation to participate in the study will be contacted at the phone number in their medical record to address any questions they may have and to confirm whether or not they will participate. Opt-out procedures include verbally indicating that they do not wish to participate.

Study participants will receive a copy of the consent document for their records. Participants will be given a signed copy of the consent document. This will be provided to them at the time of signing. The form will also be scanned into their electronic medical record.

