### F2 Schedule of Measurements

Performed at 0,3,6, and 12 month office visits.

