# G Statistical Plan

Longitudinal data from time points at 0,3,6 and 12 months will be analyzed for each component of the data collection form, including components of the patient assessment of itch and burning/pain (each on a 0-10 point scale), physician assessment for erythema and scale (each on a 0-3 scale) as well as longitudinal comparisons of measurement of the scalp involvement (distance in cm from the glabella to hairline in FFA, and area of scarring/redness/scaling in cm2 for LPP). See below for data collection form.

We predict that oral low-dose naltrexone would lead to approximately 2-3 point decrease in each of the 0-10 point patient assessments (itch and burning/pain) and a 1-2 point decrease in each of the 0-3 point physician assessments (erythema and scale). We expect the areas of scalp involvement to remain stable over the analysis period.

Patient characteristics will be summarized using descriptive statistics. The longitudinal outcomes will be analyzed using mixed model analysis to account for the correlation of measures from the same subject. Time effect will be assessed and contrasts will be used to compare mean difference between any two time points of interest. All statistical tests will be two-sided with a significance level of 0.05 and performed with SAS 9.4. Careful attention will be paid to ensuring that data satisfy assumptions required of a particular analytic strategy. When required assumptions are violated, we will explore the use of data transformations and potentially, perform some analyses using non-parametric or semi-parametric methods based on the rank of some variables.

Data on the quantitative effect size of naltrexone for LPP/FFA is limited, but based on clinical experience and descriptive case studies, we would expect patients to start at a 4-5/10 on the itch/pain/burning scales, and predict that it could decrease to 1-2/10 with

naltrexone treatment. Similarly, we expect that patients would start at a 1-2/3 on the physician assessments (erythema and scale) and predict that the physician assessments of erythema and scale could decrease to a 0-1/3. Finally, we expect the areas of scalp involvement to remain stable over the analysis period. Based on existing data showing low number of mild side effects and no serious adverse events, we plan to enroll 75-100 patients, which is the maximum number that we would expect to see over the study period given the low prevalence of disease.

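### Stable scalp extent from month 0 onward cannot show that naltrexone reduced progression, because the plan has no off-drug rate to compare it with

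*Combined protocol and SAP*

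**What the plan says.** A2 (Primary Hypothesis) asks whether 3 mg of naltrexone daily will "reduce symptoms and disease progression in patients with lichen planopilaris and frontal fibrosing alopecia". B2 (Rationale) and C1 (Primary Aim) are more cautious; B2's wording is "possibly slowing or halting disease progression".

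The design in E1 is "Uncontrolled open-label prospective study", and E3 3.c confirms that there is no comparison group. On eligibility, E2 2.a states "Adults age 18 or greater with clinically or histologically confirmed diagnosis of lichen planopilaris or frontal fibrosing alopecia are eligible". The listed exclusions add nothing about disease activity or recent worsening. Under 2.c, patients come from those with "existing and new diagnoses of lichen planopilaris and frontal fibrosing alopecia". Under 3.f they continue their other LPP and FFA medications, which may be reduced or stopped but not increased or added.

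F2 gives the measurement schedule as "Performed at 0,3,6, and 12 month office visits", and G analyses the same points: "Longitudinal data from time points at 0,3,6 and 12 months will be analyzed for each component of the data collection form". Extent is the glabella-to-hairline distance in cm for FFA, and an area in cm2 covering scarring, redness and scaling for LPP. The analysis is a mixed model with a time effect and contrasts between time points. For extent, G predicts no change: "We expect the areas of scalp involvement to remain stable over the analysis period".

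**The concern.** For itch, burning or pain, erythema and scale, the question is whether a level falls, and month 0 gives the level before treatment. Progression is different. It is a rate, and to reduce, slow or halt it is to make that rate lower than it would otherwise have been. A single reading at the start of treatment gives a level and no rate, so every rate the study can estimate is an on-treatment rate.

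This matters because the result the plan predicts for extent is stability. A1 describes the hair loss in LPP as irreversible, so for that component the hoped-for benefit is less worsening. Some entrants, particularly those with an existing diagnosis who are already on other therapy, may have been static before month 0. If so, the study's predicted success on extent would also occur on an inactive drug, and a stable result could be published as evidence of reduced progression.

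**Working it through.** **1. The plan's own figures.** The power statement at the end of G gives detectable differences of 0.7-0.8 on the patient scales and 0.21-0.25 on the physician scales, for 75-100 patients, 80% power and a two-sided paired t-test at 0.05. G states no SD. Taking the SD of the difference as range/4 (an assumption) gives 10/4 = 2.5 and 3/4 = 0.75. With difference = SD x (1.960 + 0.842) / sqrt(n):

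- Patient scales: 2.5 x 2.802 / sqrt(75) = 0.81, and 2.5 x 2.802 / sqrt(100) = 0.70.
- Physician scales: 0.75 x 2.802 / sqrt(75) = 0.243, and 0.75 x 2.802 / sqrt(100) = 0.210.

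The noncentral t gives 0.82 to 0.71 and 0.246 to 0.212. The stated figures reproduce. They do not bear on extent, for which G gives no SD, detectable change or stability margin.

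**2. What the hypothesis needs and what the plan supplies.** Let r0 be the rate of change in extent without naltrexone and r1 the rate on it. The reduction is r0 - r1.

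- r1 is estimated from months 0, 3, 6 and 12 (F2, G).
- r0 from a control group: none (E1, 3.c).
- r0 from an external or historical rate: none in the documents.
- r0 from a run-in or earlier reading: none in F1, F2 or G.
- An entry rule that would at least make r0 greater than zero: none (both 2.a sections).

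A1 describes a different schedule, with monthly visits over six months. That conflicts with F2, but it adds no pre-treatment reading either.

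**3. The predicted result, r1 = 0.** The reduction is then r0 - 0 = r0, which is whatever the reader assumes. These rates are illustrative, for FFA distance:

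| Assumed r0 (cm/year) | Observed r1 | Implied reduction (cm/year) |
|---|---|---|
| 0 | 0 | 0 |
| 0.25 | 0 | 0.25 |
| 0.5 | 0 | 0.5 |
| 1.0 | 0 | 1.0 |

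The extent data are the same in all four rows. A test of zero change at two-sided 0.05 rejects about 5% of the time in each, because r0 does not enter it.

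**4. Growth on treatment.** Suppose r1 = 0.25 cm/year. That is evidence against halting, whatever r0 is. It does not settle slowing: r0 = 0.5 implies a reduction of 0.5 - 0.25 = 0.25, and r0 = 0.25 implies 0.25 - 0.25 = 0.

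**5. FFA and LPP differ.** LPP area includes redness and scaling. G predicts that erythema and scale will improve, so LPP area can fall below its month 0 value. Such a fall is a before-after change in level, like the symptom scales. The problem in step 3 is therefore clearest for FFA distance.

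**The case against.** **The design is openly uncontrolled.** Attribution is weak for every outcome, and a fall in itch would not isolate the drug effect either. That is fair, and a single-arm study is a legitimate choice here. But a fall in itch at least shows that itch fell, whereas stable extent does not show that progression changed at all.

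**The aim is hedged.** B2 and C1 say only that slowing or halting is possible, and the power statement does not cover extent. This lowers the weight of the point. The hedge is absent from A2, however, and 3.f says that the medication rule is meant to let the investigators isolate the benefit of naltrexone.

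**Rates within treatment are available.** Four readings give three intervals (0-3, 3-6 and 6-12 months), so deceleration during treatment could be seen. All three intervals are on treatment, and none supplies r0.

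**The data collection form is not in the supplied text.** A history item on it cannot be excluded. Even so, G analyses only months 0 to 12.

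A reader might infer stronger claims that the documents do not support:

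- *That a static cohort on an inactive drug and a progressing cohort halted by naltrexone would give identical study data.* This holds only for extent. G also collects itch, burning or pain, erythema and scale, and predicts that they fall.
- *That the extent data are uninformative.* They are not: growth would count against halting, and LPP area can fall.
- *That a slope taken from earlier chart readings would identify the drug effect.* Newly diagnosed patients may have no such readings. Existing ones were not taken to protocol and may span other treatment changes, since 3.f restricts those only during the study. Patients who enter after worsening also bring regression to the mean.

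**Conclusion.** The concern holds for the extent part of A2. The planned readings estimate change in extent during treatment. They cannot show that progression was reduced, slowed or halted, and the result that G predicts is compatible with no drug effect in patients who were already static. This is separate from the absence of a stability margin: even a tight interval around zero change would leave the off-drug rate unknown.

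No figure in the documents fixes the size of the gap. Under zero on-treatment change the implied reduction equals the assumed off-drug rate, from 0 to 1.0 cm/year over the illustrative range in the working. How many entrants would be static beforehand is also unknown.

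The conclusion assumes that month 0 is the start of treatment, which is how G's before-and-after comparison reads, and that the missing form adds no earlier extent reading to the analysis. The symptom part of the hypothesis is unaffected by this point.

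**What to change.** In A2, C1 and G:

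1. Restate the extent objective as estimating the change in extent from month 0 during treatment.
2. Report that change with a 95% confidence interval, separately for FFA distance and LPP area.
3. State in advance that stable extent will not be interpreted as reduced, slowed or halted progression.

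Where dated earlier chart measurements exist, they may be reported descriptively as an exploratory pre-treatment rate. The report should note that they are incomplete, not taken to protocol and open to regression to the mean. They should not define the progression estimate.

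The first three changes are edits to wording and reporting; they need no new visits or patients. The price is a weaker claim about progression. The optional chart extraction takes staff time and would cover only a subset of patients.

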#### A3 Purpose of the Study Protocol

To outline background and procedures relating to this study.

## **B** Background

#### **B1** Prior Literature and Studies

#### Mechanism

Naltrexone is an opioid antagonist with multiple systemic pathway effects, including those involved in pruritus, wound healing, and immune system homeostasis. Low-dose oral naltrexone (doses 1-5mg daily) exhibits partial binding to  $\mu$ ,  $\kappa$ , and  $\delta$  opioid receptors, which induces a paradoxical increase in opioid receptor expression as well as of endogenous opioids,  $\beta$ -endorphins, and methione-enkephalin. In addition to effects on the opioid receptors, naltrexone also acts as an antagonist on Toll-like receptor 4, thereby producing anti-inflammatory effects through reduction of tumor necrosis factor- $\alpha$ , interleukin-6, and nitric oxide. The effectiveness of naltrexone is attributed to the widespread distribution of opioids and their receptors in the cutaneous neuroendocrine system.

#### Background

Lichen planopilaris (LPP) is an inflammatory, cicatricial alopecia, of which frontal fibrosing alopecia is considered a clinical variant. Clinical features of LPP include perifollicular erythema and scaling leading to destruction of follicular ostia and patchy scarring alopecia. In the frontal fibrosing alopecia variant, hair loss occurs on the frontotermporal region, often with associated eyebrow loss. Symptoms include pruritus, burning, pain, and tenderness. Treatment options are limited and yield inconsistent results. High potency topical steroids and topical tacrolimus are recommended as first line therapies for primary cicatricial alopecias. However, topical corticosteroids may be less effective in FFA. Other frequently utilized treatments include intralesional triamcinolone acetonide and topical minoxidil. Hydroxychloroquine and doxycycline are often used as systemic treatments in both LPP and FFA, whereas finasteride/dutasteride have been reported successfully in FFA. Overall, the level of evidence for the above treatments is limited to level IV or V evidence, and further studies into this scarring disease are needed.

Oral naltrexone is FDA approved to treat opioid dependence and alcohol use disorder at doses from 50-100mg/day. At lower doses of 1-5mg/day, naltrexone has been used off-label with success in treatment of several dermatologic conditions including lichen planopilaris. A recent case series of four patients with lichen planopilaris and a subtype, frontal fibrosing alopecia, treated with oral low-dose naltrexone at 3mg daily showed reduction of pruritus, clinical evidence of scalp inflammation, and of disease progression.

While initial studies using LDN for dermatologic conditions is promising, the level of evidence is low, generally limited to case reports and series. Recently, three excellent summaries of evidence for naltrexone in dermatologic conditions have been published. A recent review article of therapy for FFA includes naltrexone at 3 mg/day in their FFA treatment algorithm.

LDN maintain stability and efficacy through 90 days when crushed into water. One method of dosing is to crush ten 50mg tablets of naltrexone (500mg total) into 500 mL of water or juice, thus creating a 1mg/mL solution. This can be shaken prior to dispensing. At the time of reporting, this solution cost about \$15.

#### B2 Rationale for this Study

While initial studies using LDN for dermatologic conditions is promising, the level of evidence is low, generally limited to case reports and series. Based on case reports, we expect the participant to benefit though decrease in their symptoms (burning, itching) as well as decreased redness and scale and possibly slowing or halting disease progression.

This increased data would benefit society by providing further evidence for the use of low-dose naltrexone in lichen planopilaris and frontal fibrosing alopecia.

## C Study Objectives

## C1 Primary Aim

Based on case reports, we expect the participant to benefit though decrease in their symptoms (burning, itching) as well as decreased redness and scale and possibly slowing or halting disease progression.

### C2 Rationale for the Selection of Outcome Measures

A recent case series of four patients with lichen planopilaris and a subtype, frontal fibrosing alopecia, treated with oral low-dose naltrexone at 3mg daily showed reduction of pruritus, clinical evidence of scalp inflammation, and of disease progression.

## **D** Investigational Agent

- D1 Preclinical Data
- D2 Clinical Data to Date

#### D3 Dose Rationale and Risk/Benefits

See section B above.

## E Study Design

#### E1 Overview or Design Summary

Uncontrolled open-label prospective study

#### E2 Subject Selection and Withdrawal

#### 2.a Inclusion Criteria

Adults age 18 or greater with clinically or histologically confirmed diagnosis of lichen planopilaris or frontal fibrosing alopecia are eligible.

#### 2.a Exclusion Criteria

Patients with known allergy or hypersensitivity to naltrexone will be excluded. Patients will be screened for opioid use with urine screen for opioids, and any patients with positive test or concurrent use of opioids will be excluded from the study. Postmarketing reports of suicidal thoughts, attempted suicide and depression have been reported with high dose naltrexone. While no reports of mood changes have been reported with low-dose naltrexone, patients will be counseled to report any mood changes that arise during

their treatment. Patients with currently active depression, schizophrenia, and bipolar disorder will be excluded.

#### 2.b Ethical Considerations

Eligeable subjects may take naltrexone without enrolling in the study to eliminate coercion.

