#### 3.f **Prior and Concomitant Therapy**

Low-dose naltrexone, 3mg orally to be taken daily, will be prescribed. They will be continued on their other treatment medications for lichen planopilaris (LPP) and frontal

fibrosing alopecia (FFA) during the study period without increasing dose. During the study period, other LPP and FFA medications may be decreased in dose or discontinued, but will not be increased or added. This will allow the investigators to analyze the specific benefit of naltrexone.

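### The entry criteria are silent on current or recent naltrexone use, so month 0 is not secured as a pre-treatment baseline and the estimated change could be diluted

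*Combined protocol and SAP*

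**What the plan says.** All references are to the combined protocol and SAP.

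- **Inclusion (E2, 2.a):** "Adults age 18 or greater with clinically or histologically confirmed diagnosis of lichen planopilaris or frontal fibrosing alopecia are eligible". There is no condition on earlier treatment and no minimum symptom score.
- **Exclusion (E2, 2.a):** there are three grounds. On the study drug: "Patients with known allergy or hypersensitivity to naltrexone will be excluded". On opioids: "any patients with positive test or concurrent use of opioids will be excluded from the study". On psychiatric history: "Patients with currently active depression, schizophrenia, and bipolar disorder will be excluded".
- **Ethical Considerations (2.b):** "Eligeable subjects may take naltrexone without enrolling in the study to eliminate coercion".
- **Recruitment (2.c):** the pool is the institution's dermatology clinic patients "with existing and new diagnoses of lichen planopilaris and frontal fibrosing alopecia", enrolled on a rolling basis over September and October 2019.
- **Concomitant therapy (3.f):** "Low-dose naltrexone, 3mg orally to be taken daily, will be prescribed". The restriction that follows covers only the remaining treatments: "other LPP and FFA medications may be decreased in dose or discontinued, but will not be increased or added". No naltrexone-free period is set.
- **Design (E1) and Statistical Plan (G):** the study is uncontrolled and open-label. A mixed model is fitted to months 0, 3, 6 and 12, with contrasts between time points and no term or subgroup for earlier naltrexone. Patients are expected to begin at 4–5 on the 0–10 scales and reach 1–2 on the drug. Power is for a paired before-and-after comparison.

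**The concern.** Section G needs month 0 to be an untreated value, and no criterion makes it one. For a patient who has taken naltrexone for some time, the month-0 score already contains part or all of the response. With no comparison arm, nothing else in the data would show or offset this.

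Two estimates are exposed:

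- **Size of the change.** Patients who have already responded contribute little further change and pull the mean towards zero. The protocol's stated purpose is to add evidence on the drug in these two conditions, so the size of the change is a main product of the study.
- **Tolerability.** Patients still taking naltrexone at entry are more likely to be those who tolerated it. Early effects the visits ask about, such as vivid dreams and headaches, could be under-counted.

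Such patients are plausible. Section B1 reports off-label use of low-dose naltrexone in lichen planopilaris and its place in a published treatment algorithm for frontal fibrosing alopecia. Recruitment includes existing patients. With no minimum score at entry, a patient who has already improved is not screened out indirectly.

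**Working it through.** **1. Reproduce the plan's detectable differences.** Section G gives n = 75–100, a two-sided paired t-test at 0.05, at least 80% power, and detectable differences of 0.7–0.8 (patient scales) and 0.21–0.25 (physician scales). It gives no SD, only a rule of thumb from the scale range. Assume SD of change = range/4, that is 10/4 = 2.5 and 3/4 = 0.75.

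Normal approximation: difference = SD × (1.960 + 0.842)/√n.

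- Patient, n = 75: 2.5 × 2.802/8.660 = 0.81; n = 100: 2.5 × 2.802/10 = 0.70.
- Physician, n = 75: 0.75 × 2.802/8.660 = 0.243; n = 100: 0.75 × 2.802/10 = 0.210.

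The exact noncentral t gives 0.82 and 0.71, and 0.246 and 0.212. The plan's figures are reproduced. Range/6 does not fit (0.47–0.55 and 0.14–0.16).

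**2. Dilution.** Let p be the share of enrolled patients already on naltrexone, and assume they change no further. Then:

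- mean change = (1 − p) × effect;
- variance of change = SD² + p(1 − p) × effect².

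The expected effects from section G are 2–3 points (patient) and 1–2 points (physician). Every value of p is an assumption.

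| p | Patient-scale change | Physician-scale change | Power, 2-point effect, n = 75 |
|---|---|---|---|
| 0% | 2.0–3.0 | 1.0–2.0 | over 99.9% |
| 10% | 1.8–2.7 | 0.9–1.8 | over 99.9% |
| 20% | 1.6–2.4 | 0.8–1.6 | 99.9% |
| 30% | 1.4–2.1 | 0.7–1.4 | 99.4% |
| 50% | 1.0–1.5 | 0.5–1.0 | 88.8% |

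Example at p = 30%, effect 2: mean = 0.7 × 2 = 1.4; SD = √(6.25 + 0.21 × 4) = √7.09 = 2.66.

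The table's power column takes the smallest expected patient-scale effect and the smaller sample. Power there falls below 80% only when p exceeds about 56%.

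**3. The same effect seen at baseline.** Take the midpoints of the plan's expected scores, 4.5 untreated and 1.5 on treatment. At p = 20%, the month-0 mean is 0.8 × 4.5 + 0.2 × 1.5 = 3.9, and the change is 0.8 × 3.0 = 2.4 rather than 3.0.

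**4. Adverse events.** The documents give no rates for new starters or for established users, so only the direction can be argued.

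**The case against.** The strongest reply is that the plan plainly means treatment to begin at month 0. Section 3.f has naltrexone prescribed for the study alongside patients' other medicines, and section G describes a fall from untreated to treated scores. That stands: this is a missing criterion. A reader might infer that the plan intends to enrol current users, and the documents do not support that.

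A reader might also infer from section 2.b that the same clinics supply naltrexone off study and that those patients then enrol. The sentence is a safeguard against coercion. It concerns people who stay out of the study, names no prescriber and does not mention later enrolment. Supply by the same clinics is an inference. The two-month enrolment window also leaves little time to decline, start the drug, benefit and then join. None of this closes the gap for patients who were taking naltrexone before recruitment began.

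No passage says that any clinic patient is already a user, and the background describes the evidence as mainly case reports and series. So p may be small or zero, and the shares used above are illustrations only.

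Finally, dilution works against a claim of benefit and barely touches the planned test. Both are true. The remaining harm is to the reported size of the change and possibly to tolerability.

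**Conclusion.** The point holds as a gap in the entry criteria. As written they admit a patient already on naltrexone, while the analysis relies on month 0 being untreated.

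The size is a factor of 1 − p on the mean change. This rests on no further change among prior users and on a share the documents do not give. Recent starters could still improve, giving less dilution. Patients whose response is fading could worsen, giving more. A lower observed adverse-event rate is possible but cannot be quantified.

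It would be wrong to conclude that the study is underpowered. That reading fails because the expected 2–3 points far exceed the detectable 0.7–0.8. The change is worth making because it is cheap and because a pre-treatment baseline cannot be recovered after enrolment.

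**What to change.** - Add an exclusion for patients taking naltrexone at screening, or within a period before baseline that the investigators specify.
- Record prior naltrexone exposure at month 0, if the data collection form does not already do so. The form is an attachment not reproduced in the document reviewed, so this could not be checked.
- If prior users are to be allowed, say so. Base the main change from month 0 on patients not previously treated, and report prior users separately for efficacy and adverse events.
- Off-study access under section 2.b is unaffected.

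**Cost.** One eligibility line, possibly one form field, and the loss of however many current or recent users would otherwise have enrolled. Section G calls 75–100 the maximum expected, so these patients might not be replaced. At an assumed 10% the loss is about 8–10 patients (0.10 × 75 = 7.5; 0.10 × 100 = 10). At 30% it is about 22–30 (0.30 × 75 = 22.5; 0.30 × 100 = 30). Even with 52 patients left from 75, the detectable difference by the normal approximation is 2.5 × 2.802/√52 = 0.97 points on the patient scales and 0.75 × 2.802/√52 = 0.29 on the physician scales. Both are still below the smallest expected effects of 2 and 1.
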